
#### Stratification and Randomization

Those who complete the baseline assessment but are determined to be ineligible after baseline assessment will be given access to the online INSPIRE site as a courtesy. Those who meet all eligibility criteria will be randomized based on the stratification criteria described below. If any one of the following scores on baseline patient reported outcomes (PRO) is impaired, the participant will be randomized within 'Group 1,' if no scores are impaired the participant will be randomized within 'Group 0' for the primary and secondary endpoints: a) Cancer and Treatment Distress (CTXD score <0.9 vs.  $\geq 0.9$ ), b) cardiometabolic health care adherence (<80% vs.  $\geq 80\%$ ) and c) cancer health care adherence (<80% vs.  $\geq 80\%$ ). Note that each of these endpoints of the study has a measure cut-point for eligibility for Group 1 randomization required at baseline, and these are the threestratification parameters below. However, all eligible participants will be randomized

as they will all contribute data for secondary analyses. After minimum required baseline assessment is complete and eligibility confirmed, the Project Manager will fax the registration office with stratification data for randomization. Stratification factors are based on whether the participant exceeded or fell below the cut-offs for these endpoints, as determined by baseline screening values, prior to randomization. We will not stratify on age, sex, cGVHD treatment, or race/ethnicity because we believe these will be balanced adequately between study arms through random selection, and we will adjust, or stratify on these factors as needed in analyses. Participants in both groups will then be randomly assigned to either the "Control" or "Intervention" arms. The PIs and Biostatistician will review participation rates within each stratum annually and adjust the algorithm if needed. Once enrollment is complete, the sampling probability relevant to each participant will be stored in the database for use in analyses. Randomization assignment of the participant will be communicated to the participant through email. A diagram of study randomization is shown in Figure 2 and will occur as follows.

[figure not shown]
Group 1. Meets all eligibility and has one or more elevated distress or low cardiometabolic or cancer health care adherence and is randomized to one of the two groups, intervention or control.

Group 0. Meets all eligibility and does not have elevated elevated distress or low cardiometabolic or cancer health care adherence and is randomized to one of the two groups as in Group 1.

Group Y. Does not meet eligibility criteria (in active cancer treatment in the past 2 years, transplanted for disease other than hematologic malignancy or myelodysplasia, more than 5 years after first or last transplant.) Not randomized, but if consents and completes assessments (which determine final eligibility criteria) is given access to the INSPIRE online program but does not receive mailed TS-SCP, phone calls, or the follow-up assessments at 1, 3, and 12 months. .

Group X. Not randomized; consented but did not complete baseline assessment; is not given access to the INSPIRE online program but still registered with Data Management.

*Figure 2. Diagram of randomization and treatment intervention possibilities.*

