## Design

**Enrollment.** We expect to approach 1358 potentially eligible survivors who are between 2-5 years after HCT. Of these, 100 will be run-in approaches with a projected 20 enrolled and randomized, but not included in analyses. We project enrolling an additional N=492 eligible for a two-arm randomization to reach the sample sizes needed for each of the two primary endpoints. An additional projected 100 are expected to register and consent for the study, but either not complete baseline assessment required for randomization or to not be eligible for randomization after baseline assessment because of treatment in the past two years or other exclusion criteria. They will be given access to the INSPIRE site as a courtesy. We expect another group of 50 participants will consent but will not be eligible for randomization due to incomplete baseline assessment.

**Randomization.** Those with one or more targeted complications will be randomized to one of 2 arms (Group 1). Those without targeted complications will be separately randomized to one of 2 arms (Group 0). We expect approximately 305 will be eligible for Group 1 randomization and inclusion in one or more of the analyses of the 2 primary outcomes. To have sufficient power for each of the two primary endpoints, we will need to enroll 197 participants for the elevated distress outcome and 239 for the cardiometabolic non-adherence. Participants who do not qualify for analysis of either primary endpoint (Group 0) will be important for inclusion in secondary analyses and will also be randomized to intervention vs. control arms. Based on our experience in the previous internet grant, we project a loss of about 28% in the course of the study implementation from consent to 12-month assessment, 8% from mortality or severe medical problems. With 305 participants randomized to Group 1 for the primary analyses, this provides sufficient power for aims 1, 2, 3 and secondary analyses.

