For Hypothesis 1, the two primary endpoints, evaluated at the 12-month time point among the subjects identified at baseline as impaired for that particular endpoint criteria will each be compared between study arms as intent to treat analyses using standard logistic regression analyses, adjusted for cancer center and utilizing a two-sided  $\alpha=0.025$  level of significance to preserve type I error at 0.05 overall for the two primary endpoints. If other factors appear to be imbalanced between study arms, we will adjust analyses for those factors. Secondary analyses will evaluate depression alone, a PHQ-8 score  $\geq 10$  (essentially a subset of those with distress) and HCA-cancer in a similar manner as carried out for the primary endpoints. Continuous versions of the tests comprising the primary and secondary endpoints using linear regression models as well as adjusting or stratifying on engagement with the intervention (viewing at least 3 pages of the online program or completing telehealth calls) will also be carried out. Assumptions regarding normality of the outcomes will be assessed, although examination of outcomes in preliminary data suggests this is a reasonable assumption, with no significant skew in the distributions. If assumptions are not met, appropriate transformations will be implemented or alternative methods explored (e.g. non-parametric methods).

### Hypothesis 2

Characteristics of intervention arm participants at the 6-week interim assessment who require telehealth stepped care because they 1) do not meet criteria for adequate knowledge of subsequent malignancy and cardiometabolic risks, or 2) do not report improved distress, or 3) have not logged in to the online program will include those with higher depression or distress scores at baseline, more health care barriers at baseline, age 70+ years, male sex, people of color, lower income and education.

### Analysis Plan for Hypothesis 2

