### Secondary Analyses

Secondary endpoints will include depression, process measures describing internet study reach and utilization, as well as outcomes of knowledge of survivorship needs. We will compare secondary outcomes knowledge of health care needs between study arms using similar analytic methods as for the primary outcomes (both binary and continuous outcomes). We will also carry out subset analyses within stratum defined by the degree of utilization of the resources (i.e. more than one page viewed of internet site – see below for alternate definitions), and receipt of the phone calls if designated, to evaluate whether, among “users”, the tailored intervention has stronger effects.

Further analyses will identify risk factors for disparities in survivorship HCA in HCT survivors. Study reach, adoption and attrition process measures will be reported descriptively.

Primary analyses will be based on 12 month outcome measurements, but we will utilize the 3 month time point in secondary longitudinal analyses modeled after those carried out in DuHamel et al.[30] Additional secondary analyses will include evaluation of the impact of the internet intervention on continuous versions of the primary endpoints, but among all participants randomized, including those not meeting criteria for inclusion in primary analyses. This will provide estimates of the impact of study intervention on an unscreened population which would be a likely dissemination methodology.

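### The three baseline flags that stratify randomisation appear in no model whose covariates are stated; the precision lost is mainly in the continuous analyses of all randomised participants

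*Combined protocol and SAP*

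**What the plan says.** Section 7.5 (Stratification and Randomization) sets three baseline cut-offs as stratification parameters: CTXD at 0.9, HCA-cardio at 80% and HCA-cancer at 80%. It adds that "Stratification factors are based on whether the participant exceeded or fell below the cut-offs for these endpoints". The same section places participants in Group 1 (any flag impaired) or Group 0 (none), and section 12.2 (Design) says the two groups are randomised separately. The text can therefore be read as eight strata or as two.

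The primary comparisons in section 12.7 (Analysis Plan for Hypothesis 1) are made "among the subjects identified at baseline as impaired for that particular endpoint criteria", "using standard logistic regression analyses, adjusted for cancer center". Any further covariate enters by one rule: "If other factors appear to be imbalanced between study arms, we will adjust analyses for those factors". The continuous versions use linear regression, with no baseline flag or score named.

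Section 12.8 (Secondary Analyses) adds an analysis of "continuous versions of the primary endpoints, but among all participants randomized, including those not meeting criteria for inclusion in primary analyses". It names no covariates. The sponsor gives this analysis weight, because it is meant to show the effect in an unscreened population of the kind the program would probably be offered to.

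**The concern.** Stratified allocation removes between-stratum variation from the arm difference. A linear model that omits the strata still counts that variation as residual noise. Its standard error is then too large, its test rejects less often than the nominal level, and power is lost.

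Cancer center, the one covariate named in advance, is not a stratification factor. The imbalance rule does not close the gap, because it brings in factors that differ between arms and stratification exists to stop these factors differing.

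The exposure differs by analysis. In each primary set the endpoint's own flag is constant by restriction, so only the other two flags are missing. In the all-randomised continuous analyses Groups 0 and 1 are pooled, and the outcome's own flag, likely the most prognostic of the three, varies freely.

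**Working it through.** **1. The plan's own figures.** Section 12.7 gives 71 and 86 analysed per arm, two-sided α = 0.05/2 = 0.025 and 80% power for 0.52 and 0.47 SD. With n per arm = 2(z₀.₉₈₇₅ + z₀.₈₀)²/d² and no covariates:
- 0.52 SD gives 71 per arm (power 80.4% at 71).
- 0.47 SD gives 87 per arm (power 80.0% at 86).

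The relative risk of 1.9 gives 80% power if the unstated control rate is about 28% (71 per arm) or 25% (86 per arm). The stated power does not rely on the flags.

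**2. All-randomised continuous analysis, closed form.** Inputs: 492 × 0.72 ≈ 354 completers, 177 per arm; CTXD flag prevalence p = 197/492 = 0.400 (Table 3). Assumed: normal baseline score, two-sided α = 0.05, and a baseline-to-12-month correlation r, which the documents do not give.
- Effect with 80% power by the plain formula: (1.960 + 0.842) × √(2/177) = 0.298 SD.
- Share of 12-month variance explained by the flag: R² = r² × φ(c)²/[p(1−p)] = 0.622 r², where c is the cut-point on the normal scale.
- Overstatement of the SE if the flag is balanced but omitted: 1/√(1−R²).

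| r | R² | SE too large by | actual size of 5% test | power without flag | power with flag |
|---|---|---|---|---|---|
| 0.5 | 0.156 | 9% | 3.3% | 82% | 86% |
| 0.6 | 0.224 | 13% | 2.6% | 83% | 89% |
| 0.7 | 0.305 | 20% | 1.9% | 84% | 92% |

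For HCA-cardio (p = 239/492 = 0.486) the factor is 0.636 instead of 0.622, and the results are nearly identical.

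**3. The same analysis with attrition and both readings of the strata.** The closed form assumes perfect balance among completers. The trial balances the 492 randomised and then loses 28%, which undoes part of the balance. Simulating that sequence for CTXD with random loss and r from 0.5 to 0.8:

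| Strata | SE too large by | actual size of 5% test | power at 0.298 SD, without → with flags |
|---|---|---|---|
| Eight flag combinations | about 7-20% | about 4% falling to 2% | 81-84% → 86-95% |
| Group 1 / Group 0 only | about 1-5% | about 4-5% | 79-80% → 84-94% |

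**4. Primary logistic analyses.** 4,000 simulated trials per setting, stratified on the two flags that still vary (45% prevalence assumed), relative risk 1.9, α = 0.025. Assumed control rates were 25.7% (CTXD) and 22% (HCA-cardio), so power starts below 80%. Center was not modelled.

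| Odds ratio of each other flag | CTXD power, without → with | HCA-cardio power, without → with |
|---|---|---|
| 1 | 72.1% → 73.0% | 71.5% → 71.9% |
| 1.5 | 72.7% → 74.2% | 71.5% → 72.5% |
| 2 | 72.6% → 75.3% | 72.3% → 74.7% |
| 3 | 74.2% → 79.2% | 72.4% → 76.6% |

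At an odds ratio of 3, the unadjusted test rejects 1.9% of the time under no effect, against 2.5% nominal, for both endpoints. The standard error of the log odds ratio does not shrink when the flags enter. For CTXD at an odds ratio of 2 it rises from 0.365 to 0.380. The gain comes from a test nearer its nominal level and from an effect estimate that is less attenuated.

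**5. Continuous analyses in the impaired subsets.** If the other two flags explain 1% to 10% of the variance, power rises from 80% to about 80-85%.

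**The case against.** Several points can be made for the plan as written.

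- *The primary analyses already condition on the flag that matters most.* This stands. Restriction to impaired participants holds the endpoint's own flag constant. The documents give no association between, say, an adherence flag and later distress, so the primary gain could be zero.
- *The strata may be only Group 1 and Group 0.* This also stands as a possible reading. The SE overstatement then falls to about 1-5%, and no stratum varies within a primary set. The power gain in the all-randomised analysis survives, but it is then mostly ordinary prognostic adjustment and owes little to the stratification.
- *Other text may bring the flags in.* It does not. The section 7.5 remark about adjusting in analyses concerns age, sex, cGVHD treatment and race/ethnicity, the factors not stratified on. The stored sampling probability is tied to no model. The imbalance rule could admit a flag if attrition upset the balance, but only after the data are seen.
- *The all-randomised analysis is secondary, with no stated alpha or power target.* True, and this limits the weight of the point.

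A reader might infer that the trial is underpowered as stated, that the primary standard errors are too wide, or that no planned analysis at all uses the flags. The documents support none of these. The 80% figure reproduces without covariates. The primary models are logistic, where adding the flags raises the log-odds-ratio standard error. The covariates of the longitudinal models in section 12.8 are set by reference to a cited trial and cannot be checked.

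**Conclusion.** The point holds as a free improvement. No analysis with stated covariates includes the three stratification flags, and the imbalance rule is unlikely to add them. In the all-randomised CTXD analysis, including them is worth roughly 5 to 14 points of power at 0.298 SD (79% to 84% at the low end of the two-strata range, 80% to 94% at its high end). In the primary logistic analyses it is worth about 0 to 5 points.

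The omission makes tests conservative. It introduces no bias in the arm comparison and no excess type I error, and it does not undermine the stated power.

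The sizes rest on assumptions outside the documents: correlation 0.5 to 0.8, odds ratios 1 to 3 for the other flags, the control rates above, a 5% level for the secondary analysis, and loss unrelated to outcome. The calculations do not model the multiple imputation that section 12.7 plans if attrition exceeds 10%.

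**What to change.** Add to sections 12.7 and 12.8: *All arm comparisons include the baseline CTXD, HCA-cardio and HCA-cancer stratification flags; a flag that is constant in an analysis set is dropped.* If only one place can be changed, it should be the all-randomised continuous analyses in 12.8. In section 7.5, state whether the strata are the eight flag combinations or Group 1 and Group 0 only.

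The cost is two extra terms in each primary model and three in each all-randomised model. The flags are known for every participant before randomisation, so no new data are needed. The one consequence to state is that the odds ratio in the logistic models becomes conditional on the flags, and so is a slightly different quantity from the unadjusted one. Fixing the covariates in advance also leaves less to be settled by the undefined imbalance rule.

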## Blinding

To reduce potential for contamination of the treatment and control conditions, the site investigators and NMDP study coordinators who contact survivors to respond to study questions or for incomplete assessments will be blinded to randomization. Information on randomization will be kept separate from the other data in a protected file viewable only to investigators and study staff who have intervention contacts with participants.

## Participant Randomization Notification

To maintain randomization blinding of NDMP study coordinators completing the study assessment contacts with participants and study status tracking, the Project Manager will email survivors their randomization with internet site link and contact reminders for questions. She will give all participants the options to call the study toll-free line or the Coordinating Center with any questions.

## Treatment

### Intervention: Full Internet Program Access

*Treatment Internet Site and Related Materials.* The INSPIRE internet site will be continuously available to the participant for the study year. It will consist of the following six levels: 1) A greeting home page, with links to each target area. 2) Lift Mood, emphasizing managing stress and emotions. 3) Boost Heart Health pages focusing on implementation of the SCP addressing overall health behavior recommendations with a focus on cardiometabolic health. 4) Prevent Cancer pages focusing on implementation of the SCP for cancer screening tests and behaviors that prevent cancer. 5) Getting Connected, focusing on social activation and using resources to improve mood. 6) Tips and Tools, with downloadable content and tracking worksheets for monitoring progress on goals. There will also be options for participants to send secure messages with questions or comments on any topic to the study and links to the study Facebook page maintained and monitored by the study staff. The secure Facebook page will offer notices and encourage return to the site. Twitter and Instagram will have the same messages. We will increase motivation by email 'pushes', and mobile application notifications to cue survivors to links that match needs, and encourage use and tracking of the SCP. After completing the 12-month assessment, participants will receive a \$25 gift card from Amazon, to be mailed to them as study payment.

*Tailoring* will include: 1) use of the participant's first name on logins, 2) recommended links to site landing pages specific to the participants' baseline elevated scores, 3) participants will receive tailored 'push' email links at 8 times after randomization, and 4) participants will receive mailed individualized TS-SCP with information about their cancer treatment and current recommended preventative health care guidelines. Health care providers listed on the baseline assessment will be sent as TS-SCP with an abbreviated listing of the recommended SCP screening and a focus on cardiometabolic health and cancer screening.

*Stepped Care Self-Management Telehealth Contacts.* Group 1 intervention participants who at the T2 (6 weeks) indicate no use of the online program, or lack knowledge of their cardiometabolic or subsequent malignancy risks, or do not indicate improvement in distress, will receive telehealth contacts. These will be three to four calls via phone. Calls will last 20-30 minutes for the first call and 10-20 minutes for the 'booster' calls. They will be led by a 'coach' trained by the clinical investigators in HCT and self-management skills, using a manual to deliver call content focused on assisting survivors with using the self-management skills in the online program. This is a brief, manualized intervention is designed to be sustainable without extensive clinical training and has been tested. The first session will focus on impairments indicated by the T2 6-week screening PRO. The coach and participant will make shared decisions, led by the participant, on goals and an action plan for addressing deficits, and elicit potential barriers and their solutions based on chronic disease self-management models (Figure 1).[1, 84, 133, 140-143] The second and third 'booster' calls will review progress on the action plan, address barriers and agree on a revised plan if needed. Participants and coaches will decide whether a fourth call would be helpful based on the complexity and difficulty of the goals and action plans. The contacts will be audiotaped for process evaluation

of content and fidelity to the self-management script.

#### Control: Website with Links and Delayed Internet Program Access

Participants randomized to receive the website providing links to existing transplant and cancer survivor sites and delayed access to the INSPIRE internet program (control) arm will be notified that they will be able to access the secured internet content after one year, and in the meantime will be provided with links to existing online resources and survivor sites. They can access the study content after they have completed their 12-month outcome assessments. At that time, the Project Manager will have their web permissions modified so that all internet study content can be accessed until the study closes. Internet site access will be as described above in 7.5.1. Control participants will also receive mailed individualized TS-SCP at randomization. After completing the 12-month assessment, control participants will also receive a \$25 gift card from Amazon, to be mailed to them as study payment.

#### Group Y Website Access

Survivors who do not meet inclusion criteria will be ineligible for randomization. These survivors will, however, have full access to the internet site if they have completed the required baseline assessment. But they will not receive the mailed TS-SCP or the follow-up assessments at 1, 3, and 12 months.

#### Group X

Survivors who have consented to participate but not completed the baseline assessment cannot be randomized and cannot access the study internet content at any point.

## 8.0 EVALUATION

Table 1. PRO Measures and schedule of administration (T2 for intervention-only participants described in section 8.1)

8.1 Patient Reported Outcome Measures	T1 Baseline Screening	T3 3 month Outcome	T4 12 month Outcome
Primary Outcomes			
Cancer and Treatment Distress (CTXD)	X	X	X
Health Care Adherence (HCA)	X		X
Secondary Outcomes			
Patient Health Questionnaire-8 Depression (PHQ8)	X	X	X
Moderators and Risk Factors			
Computer and Mobile Phone Use	X		
Background: potential barriers to PCA (age, income, rural/urban, gender, cancer and treatment history, current medical history, medications)	X		
GVHD Symptom Scale (allogeneic only)	X		
Medical Comorbidities and Medications	X		X
Mediators			
Knowledge of Survivorship Needs	X	X	X
Health Self-Efficacy	X	X	X
Study Evaluation			
Evaluation of Program and Participation			X
ESTIMATED TIME REQUIRED	30-40	10-15	25-35

